### 3. Study Design

**Specific Aim 1: To determine the burden of CT and NG infections and correlates of infection among asymptomatic pregnant women in Gaborone, Botswana.**

Title: The diagnosis and treatment of *Chlamydia trachomatis* and *Neisseria gonorrhoeae* in pregnant women to prevent adverse neonatal consequences."

**Methods and Procedures:** To accomplish Aim 1, we will conduct a cohort study among antenatal patients at collaborating Greater Gaborone District Health Management Team (DHMT) clinic sites (STI testing clinics). First, 1(a): Use diagnostic testing to estimate the prevalence of CT/NG infections at the 1st antenatal care visit, a 3rd trimester visit, and the 1st postnatal care visit; and estimate the incidence of infections between visits. 1(b): To assess the correlates of infection, including sociodemographic and behavioral factors (e.g. alcohol use), obstetric and medical information (e.g. HIV status), sex partner characteristics, and partner notification and treatment outcomes.

**Recruitment and Eligibility:** We will recruit 250 study participants from pregnant women presenting for antenatal care services at designated study 'testing' clinics in Gaborone. Eligibility/Inclusion criteria (also described in Section E) include: 1) Age  $\geq$  15 years, 2) Currently pregnant, 3) Attending first ANC visit, 4) 27 weeks of gestation or less, 5) Not currently experiencing CT/NG-related symptoms (determined by validated screening tool), 6) Not treated for CT/NG in the past 30 days 7) Willingness to provide self-collected specimens for CT/NG testing (at three time points), 8) Willingness to return for a test of cure (if test positive during antenatal care), 9) Will reside in Gaborone through the time of delivery and 1st postnatal visit, 10) Willingness to have neonates tested for CT/NG at their first postnatal visit, And 11) Mentally competent to understand the informed consent.

Patients will be screened for eligibility via obstetric chart review at the time of the appointment. Those who are ineligible due to STI-related symptoms will be flagged and identified for healthcare providers to assess for syndromic management (standard care). All eligible patients will be provided information about CT and NG infections and study risks and benefits. Those providing informed consent will be enrolled, instructed on how to self-collect a CT/NG specimen and asked to share several forms of detailed contact information to assure follow-up. Reasons for ineligibility will be logged with age, gestational age, and reason for ineligibility, to assess generalizability. Similar data and reasons for decline will also be recorded.

A sample of up to 20 sex partners will be recruited for participation in a brief semi-structured interview. Partners will be recruited through the following channels a) snowball recruitment via study participants who give informed consent to contact their partner(s) b) sex partners presenting to a study clinic for STI treatment using a contact slip c) sex partners contacting the study team via contact information provided with EPT materials d) partners attending antenatal or postnatal care visits with partners. Eligibility criteria include 1) Age  $\geq$  15 years 2) Sex partner of a pregnant women being treated for CT, NG, Syphilis, or an STI syndrome 3) Willing to complete a recorded semi-structured interview and 4) Mentally competent to understand the informed consent.

A sample of up to 20 stakeholders will be recruited for participation in a brief semi-structured interview. Eligibility criteria include 1) a stakeholder, defined as a clinician who provides antenatal or sexual and reproductive healthcare, OR a program manager at a clinic that provides sexual and reproductive healthcare, OR a policymaker in the field of maternal and sexual and reproductive health and 2) Willing to complete a recorded semi-structured interview.

**Specimen Collection, Transport, Processing and Storage:** Specimens will be labeled with a unique study ID by trained study staff, who will place them in secure storage for up to 24 hours at 2° - 30°C until testing.

**Laboratory Testing:** CT /NG testing: will be performed using Xpert® CT/NG assay [Cepheid, Sunnyvale, CA] by trained staff. All specimens will be run on-site with standard controls, per manufacturer's instructions. (See Aim 3 for quality control). (Note: The Xpert is currently being used in Botswana for TB testing).

Title: The diagnosis and treatment of *Chlamydia trachomatis* and *Neisseria gonorrhoeae* in pregnant women to prevent adverse neonatal consequences.”

**Reporting and Treatment:** Antenatal CT and NG testing will be conducted at enrollment (1st ANC), during the third trimester, and at the 1st postnatal visit (See Figure 1). Results and treatment will be provided in the same way at each time period. **Results:** All participants will receive results on the same day as testing (in person or by phone). **Treatment:** Appropriate clinical staff will provide treatment per the Botswana MoH STI treatment protocols. Treated participants for CT/NG will be asked to provide a second specimen at least 4 weeks after treatment to document treatment outcome (test of cure). Test results will be recorded by study staff in the patients' treatment record files as well as into the study dataform. **Partner Services:** All study staff will be trained on appropriate and effective methods for counselling women on how to communicate test results to partner(s) in a nonthreatening and blameless manner. (For example, it's important to clarify that the duration of sexually transmitted infections during pregnancy is unknown, many infections are asymptomatic, and infections do not have implications about partner fidelity). Additionally, participants will be given several options for partner services: 1) No disclosure: In the case of risk for intimate partner violence (IPV). 2) Supportive disclosure: where the participant is assisted by trained study staff either in person or over the phone in notifying their partners. Also, participants will be given the option of bringing partners to the study clinics for counselling and treatment. 3) Expedited partner therapy for CT/NG treatment: where the participant can bring treatment to partners prior to examination by a healthcare provider. **IPV:** will be proactively assessed and managed for all participants, not only those testing STI positive. To that end, we will use a validated screening tool adapted from Rabin RF et al. to assess participant risk for intimate violence and other negative partner responses to notification of an STI. Based on the screening results, when appropriate, IPV risk will be mitigated by referring women to local support services available in the country for free counseling and support, the NGO Botswana Family Welfare Association (BOFWA; <http://www.bofwa.org.bw/>). We will also provide a 24-hour emergency contact line through which participants can receive information and support and referrals in general.

**Data collection:** Participants will be asked to respond to a survey on socioeconomic characteristics, relationship status and sexual history (e.g. number of condomless sex acts), other risk behaviors (e.g. alcohol use), obstetric/medical history, and prior STI symptoms and treatment in the past year. A sub-set of participants will be asked additional questions on partner notification and treatment experiences postnatally. A data collection instrument will be used to abstract obstetric, and medical information from the patient-held and clinic records, including receipt of syphilis testing, results and titre, and treatment.

The sample of sex partners will participate in a brief semi-structured interview on partner notification and treatment experiences. The sample of stakeholders will participate in a brief semi-structured interview on antenatal diagnostic testing for chlamydia and gonorrhea, point-of-care syphilis testing, and STI expedited partner therapy.

Specific Aim 2: To compare longitudinal neonatal outcomes for pregnant women tested & treated for CT/NG infections with women who received standard antenatal care.

**Methods and Procedures:** Simultaneously with Aim 1, 250 antenatal patients at designated study 'standard of care' clinics will be enrolled as a comparison group receiving the standard care with additional partner services. At standard of care clinics, CT/NG testing will be offered to mothers and neonates at the 1st postnatal visit for all 500 participants to accomplish 2(a): To estimate the frequency of vertical transmission of CT/NG infections and adverse neonatal outcomes and association with maternal testing and treatment. And subaim 2(b): To assess independent factors associated with adverse neonatal outcomes and control for these factors in the analysis. Exposure measures will include maternal sociodemographic, behavioral, obstetric, and medical information, and partner treatment, and adverse perinatal outcomes (e.g. low birth weight).

Title: The diagnosis and treatment of *Chlamydia trachomatis* and *Neisseria gonorrhoeae* in pregnant women to prevent adverse neonatal consequences.”

**Recruitment/Eligibility:** Women will be similarly recruited and enrolled, and eligibility criteria are identical to those in the STI testing group (see Aim 1). Those who are ineligible due to STI-related symptoms will be flagged and identified for healthcare providers to assess for syndromic management (standard care). All eligible patients will be invited to participate, and those providing informed consent will be enrolled. The comparison group will receive the standard of care for management of STIs during antenatal care with additional IPV screening and partner services offered to those in Aim 1. As in Aim 1, a data collection instrument will be used to collect sociodemographic and behavioral factors, and obstetric/medical information, and data will be abstracted from the patient-held and clinic records. All mothers will be provided with informed consent for their neonate’s participation at enrollment.

Postdelivery, study staff will provide an updated verbal consent to mothers to collect and tests neonatal specimens.

**Laboratory testing:** All participants will test for CT/NG infection using the Xpert® CT/NG assay at the first postnatal visit using self-collected swabs. Women testing positive will receive antimicrobial treatment with options for partner treatment described in Aim 1. For neonates of mothers testing positive for CT/NG, the study follow-up nurse will collect ocular and nasopharyngeal swab samples for testing of CT/NG transmission using the Xpert® CT/NG assay. Studies have demonstrated the efficacy of PCR tests for infant diagnosis using ocular and nasopharyngeal swabs. Infants testing positive will receive treatment according to Botswana guidelines (20mg/kg of azithromycin (liquid formulation) for CT, injection of 50mg/kg of ceftriaxone for NG) and referrals. Efforts will be made to provide same-day results.

**1st Postnatal Visit Survey :** Primary outcome will be collected by the study follow-up nurse and include: CT/NG test result from neonate ocular/nasopharyngeal swabs. Secondary outcomes include clinical evidence or records of conjunctivitis and history of pneumonia identified in interviews or medical charts; and inpatient length of stay. Data on potential confounders will be collected from three sources: 1) Interviewer-administered survey, AND 2) Patient obstetric record, OR 3) Hospital/clinic records. (Study staff have experience with all 3 sources). If new neonatal conditions are identified, the nurse will ensure necessary referrals.

**Retention and Follow -up:** Multiple forms of contact information will be collected at enrollment for all participants to ensure retention. All study visits will take place during regularly scheduled antenatal and postnatal care visits. Participants will be requested to give permission for communication through text messages, which will remind about upcoming visits. Participants who do not return for scheduled visits will be actively contacted by both clinic and study staff and encouraged to return for care. The study team will follow-up with all participants weekly around the expected date of delivery and participants will be encouraged to notify the team of first postnatal visit. Ten attempts will be made through various contact methods.

**Specific Aim 3:** To assess markers of inflammatory response to CT/NG infection during pregnancy and associations with vertical transmission of CT/NG.

**Methods and Procedures:** At the baseline, third trimester, and 1st postnatal care visit, self-collected vaginal swabs and EDTA plasma samples will be collected from all participants in the STI testing group, and used to measure cytokine concentrations. Cytokines will be identified using the Luminex xMAP® 48-plex assay method located at Stanford University in order to accomplish 3(a): To test immunologic factors associated with vertical CT/NG transmission by describing concentrations of inflammatory cytokines in participants who tested positive for CT/NG. A secondary analysis of data collected during maternal CT/NG testing at the first postnatal visit (Aim 2) will be performed to accomplish 3(b): To determine the association between the Xpert® CT/NG assay’s pathogen-specific cycle threshold value (Ct), which is a marker for the burden of infection, and vertical transmission of

Title: The diagnosis and treatment of *Chlamydia trachomatis* and *Neisseria gonorrhoeae* in pregnant women to prevent adverse neonatal consequences.”

CT/NG to neonates; and 3(c): To assess the frequency and distribution of Sample Adequacy Control (SAC) cycle threshold ( $C_t$ ) values from the Xpert® CT/NG assay, which may be a marker of inflammation, and evaluate correlations with the transmission of CT/NG to neonates.

**Recruitment/Eligibility:** Eligibility criteria for the comparison group are identical to those in Aims 1 and 2. Data will only be collected from participants in the STI testing group.

**Specimen Collection, Transport, Processing and Storage:** A self-collected swab for cytokine measurement will be collected at the baseline, third trimester, and first postnatal care visit and stored at -80°C. A peripheral blood sample (2-4mL) will be collected at the baseline, third trimester, and postnatal study visits. The blood sample will be processed and aliquots of EDTA plasma will be stored at -80°C. The swabs and plasma samples will be transported in dry ice to Stanford University for processing. Luminex will be used to measure the concentrations of 48 cytokines in the 48-plex assay (including IL-1 $\alpha$ , IL-1 $\beta$ , IL-6, IL-7, IL-8, IL-10, granulocyte macrophage colony- stimulating factor [GM-CSF], interferon- $\gamma$  inducible protein [IP]-10, monocyte chemoattractant protein [MCP]-1, MIP-1 $\alpha$ , MIP-1 $\beta$ , and tumor necrosis factor [TNF]- $\alpha$ ). These cytokines were selected based on previously identified associations with genital infection. Additionally the pathogen-specific and SAC Ct results will be automatically generated for each self-collected vaginal sample tested using the Xpert® CT/NG assay at delivery.

**Laboratory Testing :** Once the specimen is collected, study staff will follow instructions for sample preparation and testing. Luminex assays enable fast and accurate cytokine measurements by utilizing specially prepared microspheres, internally dyed with a graded mixture of red or infrared fluorescent dyes. Varying the degree to which the beads are internally dyed creates hundreds of different fluorescent profiles that can be individually interrogated and classified in a single sample. The BHP lab in Gaborone can conduct cytokine analysis using an ELISA quantitative; however, this assay is currently limited to only IL-6, ICAM1, and VCAM. Further, the ELISA is a single assay and sample processing would be costly and time-consuming compared to the Luminex multiplex assay.

**Specific Aim 4:** To determine the acceptability, feasibility, and costs of implementing point-of-care (PoC) syphilis testing and treatment among pregnant women in Botswana by offering: 1) dual HIV and syphilis PoC testing for pregnant women who are HIV uninfected/undiagnosed and 2) PoC syphilis testing for pregnant women with a known HIV infection with same-day treatment to women in the designated PoC clinic. PoC testing will be offered in addition to routine syphilis and HIV testing.

**Methods and Procedures:** An additional 200 antenatal patients at the designated PoC clinic and 200 at the ‘standard of care’ clinic will be enrolled (400 total). In the PoC clinics, participants who are HIV uninfected/ undiagnosed will be offered PoC dual HIV/syphilis testing and women living with HIV will be offered a PoC syphilis test. PoC participants will receive same-day results and treatment. Participants in the standard of care clinic will continue to receive the usual care.

Additionally, analysis will incorporate the data from 200 participants previously enrolled in the CT/NG parent study. These data will be used as a “pre-test” and will include all 100 women enrolled in the standard of care clinic and all 100 women enrolled in the PoC testing clinic.

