## 2. Specific Aims:

- a. **Specific Aim 1:** To determine the burden of CT, NG infections and correlates of infection among *asymptomatic* pregnant women in Gaborone, Botswana.
  - i. 1(a): Use diagnostic testing to estimate the prevalence of CT/NG infections at the 1st antenatal care visit, a 3rd trimester visit, and the 1st postnatal care visit; and estimate the incidence of infections between those visits.
  - ii. 1(b): To assess the correlates of infection, including sociodemographic and behavioral factors (e.g. alcohol use), obstetric and medical information (e.g. HIV status), and sex partner characteristics.
- b. **Specific Aim 2:** To compare longitudinal neonatal outcomes for pregnant women tested & treated for CT/NG infections during antenatal care with women who received standard antenatal care.
  - i. 2(a): To estimate the frequency of vertical transmission of CT/NG infections and subsequent neonatal outcomes (e.g. ophthalmia neonatorum) and the association with maternal testing and treatment during antenatal care.
  - ii. 2(b): To assess independent factors that may be predictive of adverse neonatal outcomes and control for these factors in the analysis. Exposure measures will include maternal sociodemographic and behavioral factors (e.g. alcohol use), obstetric and medical information (e.g. HIV status), partner characteristics, and adverse perinatal outcomes (e.g. low birth weight).

- c. **Specific Aim 3:** To assess the burden of infection and markers of inflammatory response to CT/NG infection during pregnancy and associations with vertical transmission of CT/NG.
  - i. 3(a): To test immunologic factors associated with vertical transmission of CT/NG by describing concentrations of genital inflammatory cytokines in participants who test positive for CT/NG.
  - ii. 3(b): To determine the association between the Xpert® CT/NG assay's pathogen-specific cycle threshold value (Ct), a possible marker for burden of infection, and vertical transmission of CT/NG to neonates.
  - iii. 3(c): To evaluate the frequency and distribution of Sample Adequacy Control (SAC) cycle threshold values (Ct) from the Xpert® CT/NG assay, which are a measure of tissue inflammation, and evaluate any correlations with the transmission of CT/NG to neonates.
- d. **Specific Aim 4:** To determine the acceptability, feasibility, and costs of implementing point-of-care (PoC) syphilis testing and treatment among pregnant women in Gaborone, Botswana.

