### b. Inclusion/Exclusion Criteria:

#### • Inclusion Criteria:

- Age  $\geq$  15 years,
- Currently pregnant,
- Attending first ANC visit,
- 27 weeks gestation or less
- Not currently experiencing CT/NG-related symptoms (determined by validated screening tool),
- Not treated for CT/NG in the past 30 days,
- Willingness to provide self-collected specimens for CT/NG testing (for the STI-testing group, this will take place at their first ANC visit, at another visit in their third trimester,

Title: The diagnosis and treatment of *Chlamydia trachomatis* and *Neisseria gonorrhoeae* in pregnant women to prevent adverse neonatal consequences."

and at postnatal care. For the standard of care group, samples will only be collected at postnatal care),

- Willingness to return for a test of cure if CT/NG test is positive during antenatal care,
- Will reside in Gaborone through the time of delivery and 1st postnatal visit,
- Willingness to have neonates tested for CT/NG at their first postnatal visit,
- Mentally competent to understand the informed consent.

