**d. Potential Benefits:**

**Conducted by study personnel:**

Diagnosis and treatment of CT/NG may prevent the development of future complications in reproductive health as well as transmission of undiagnosed infections to newborns and sexual partners, and reduce the risk of adverse birth outcomes. Diagnosis and treatment of CT/NG may address symptoms among infants. Participants in the syphilis PoC testing clinics will have access to rapid syphilis results, which may increase the likelihood of treatment access for those who test positive and may reduce the need for non-routine follow-up visits.

Potential benefits to society include determination of the benefits (in terms of infections cured and prevention of vertical transmission of STIs and subsequent adverse outcomes) of integration of routine CT/NG screening into antenatal care in Botswana. The study will also provide valuable operational data regarding of patient follow-up and treatment, as well as insights into the formation and revision of antenatal care policies, guidelines and funding levels. Results will serve to estimate prevalence of CT/NG infections among asymptomatic pregnant women in Gaborone, Botswana.

**Risk/Benefit Ratio:** The benefits to the participants in diagnosis and treatment of CT/NG infection outweigh the risks of physical or personal discomfort from specimen collection. As syphilis testing is already part of the standard of care, there are no additional testing risks. As described above, confidentiality of study data will be rigorously maintained. The benefits of PoC syphilis testing include same day results and treatment.

**12. Therapeutic Alternatives:** Participation in the study protocol is voluntary. Patients declining participation will still receive treatment from their physician, including STI screening, according to current standards of care.

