Statistical Plan: Evaluating the diagnosis and treatment of *Chlamydia trachomatis* and *Neisseria gonorrhoeae* in pregnant women to prevent adverse neonatal consequences in Gaborone, Botswana

ANALYSIS

Primary outcome measure

- Mother-to-child transmission of CT and/or NG: Neonates of mothers who test positive for CT and/or NG infections will be tested using both ocular and nasopharyngeal specimens.

Secondary outcome measures

- Pregnancy outcome
 - o Miscarriage, defined as pregnancy loss before the 20th week of gestation, will be identified through self-report by the participants, and the medical record.
- Perinatal outcome
 - o Stillbirth, defined as fetal death at or after 20 weeks gestation and prior to delivery, will be identified through self-report by the participants, and the medical record.
- Neonatal outcomes
 - o Preterm birth, defined as delivery prior to 37 weeks' gestation, will be identified through the obstetric record and/or
 - o Low birth weight, defined as birth weight of less than 2500g, will be identified through the obstetric record.
 - o Conjunctivitis, defined as the presence of swollen eyelids and pus in eyes, will be identified during the care visit by the follow-up nurse/midwife.
 - o Pneumonia, defined as cough or difficult breathing plus at least one of the following: Fast breathing, Lower chest wall indrawing. In addition, either crackles or pleural rub may be present on chest auscultation.
 - o We will also ask mothers about prior neonatal symptoms and review the obstetric record.
- Maternal outcomes
 - o CT and NG infections: The prevalence of maternal CT/NG infections will be assessed among participants in the testing group at baseline and during the third trimester.
 - o The incidence of infections between baseline and follow-up in the testing group.
 - o Individual cytokines and groups of cytokines associated with mother-to-child transmission of CT/NG, preterm birth, and low birth weight.
- Economic outcomes
 - o The total cost of the CT/NG test and treatment intervention for asymptomatic pregnant women.
 - o The costs per woman tested, treated, and cured; and the incremental costs per adverse neonatal outcome averted (e.g. neonatal CT/NG infections, preterm birth, and low birth weight) comparing the testing intervention with syndromic management.

Statistical analysis

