Prevalence of each STI will be measured as the proportion of individuals testing positive for a given STI divided by the number of individuals tested at each time point. Exact binomial 95% confidence intervals for prevalence will be estimated. Incident infections will be identified when a participant tests negative for an STI during her first ANC visit and positive for an STI during follow-up visits. Time at risk will be the length of time between the first test date and the positive test date. Correlates of CT/NG infections will be identified using both bivariate analyses and multivariate analyses.

Our primary outcome (mother-to-child transmission of CT and NG) and secondary outcomes (composite of preterm birth and/or low birth weight, and prevalence of maternal CT/NG infection at delivery) will be assessed using intention to treat analysis at the clinic level. We will conduct both unadjusted and adjusted analyses, including risk factors for maternal STI and neonatal infection that may be imbalanced between the testing and standard-of-care clinics. Effect measures will be estimated with 95% confidence intervals. All analyses will be carried out using the latest version of Stata statistical software (17.0 or higher; College Station, TX, USA).

To assess immune/inflammatory markers, multiple logistic regression models will be developed in an iterative process to identify individual cytokines and groups of cytokines associated with mother-to-child

transmission of CT/NG, preterm birth, and low birth weight. Additionally, we will identify plasma cytokine signatures that classify study participants with or without preterm birth/low birth weight infants.(1) We will define three equal frequency tertiles or “bins” (low, medium, and high), using all plasma samples. Next, we will use the VSURF R package, a random forest method to select the most predictive cytokines to differentiate samples from participants with and without preterm birth/low birth weight infants.(2) From these, we will build a decision tree to classify the samples. To better calibrate the accuracy of the decision tree, we will perform permutation testing.

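### The adjusted testing-versus-standard-care analyses are not limited to pre-intervention covariates, so low birth weight (itself a SAP outcome) and partner treatment could both be entered

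*Protocol*

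**What the plan says.** Specific Aim 2 compares neonatal outcomes between women tested and treated antenatally and women under standard care. Its sub-aim 2(b) in Protocol section 2 is "To assess independent factors that may be predictive of adverse neonatal outcomes and control for these factors in the analysis". Protocol section 3 (Specific Aim 2, Methods and Procedures) then lists the candidates: "Exposure measures will include maternal sociodemographic, behavioral, obstetric, and medical information, and partner treatment, and adverse perinatal outcomes (e.g. low birth weight". Section 2 also names low birth weight, but has partner characteristics where section 3 has partner treatment. Under the first postnatal visit survey, section 3 adds: "Data on potential confounders will be collected from three sources". No cut-off before the intervention is given.

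The SAP's secondary outcome list includes "Low birth weight, defined as birth weight of less than 2500g, will be identified through the obstetric record". Its statistical analysis section compares the groups on the primary outcome and on two secondary outcomes, the "composite of preterm birth and/or low birth weight, and prevalence of maternal CT/NG infection at delivery". It plans unadjusted and adjusted analyses without naming either as primary. The adjusted ones are described as "including risk factors for maternal STI and neonatal infection that may be imbalanced between the testing and standard-of-care clinics". There is no covariate list.

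Two further places bear on timing. Protocol section 11.d says that diagnosis and treatment may prevent, among other things, "transmission of undiagnosed infections to newborns and sexual partners, and reduce the risk of adverse birth outcomes". Protocol section 5.b says: "For the standard of care group, samples will only be collected at postnatal care".

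**The concern.** A covariate in an adjusted group comparison should not be something the intervention can change. If it is, the model removes part of the effect being estimated and can introduce bias through unmeasured causes of both covariate and outcome. The likely direction is towards no effect, but that is not certain.

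Low birth weight and partner treatment are both open to this. The plan treats low birth weight as something testing may reduce, and the SAP's economic analysis counts it as an outcome averted. Partner services are offered in both groups, but only the testing group receives an antenatal study result that can prompt partner treatment before delivery. Partner treatment is therefore expected to differ between groups by design, and a rule that looks for imbalance could select it for that very reason.

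The composite raises a sharper problem. Every low-birth-weight infant has the composite outcome by definition, so adjusting for low birth weight conditions on part of the outcome.

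Groups are formed by designated clinics and no randomisation is described. Readers will therefore set the adjusted estimate beside the unadjusted one.

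**Working it through.** **Inputs from the SAP (Sample size):** transmission 5% under standard care and 0.7% with testing; 232 evaluable women per arm.

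**Inputs assumed, because the documents give no rates:** low birth weight 15% under standard care and 10% with testing; risk ratio k of low birth weight for neonatal infection from 1 to 5; preterm birth without low birth weight 6% of infants under standard care, and either 6% (scenario A) or 4% (scenario B) with testing.

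**The plan's own figures.** The planned risk ratio is 0.007/0.05 = 0.14, a reduction of 86%, which agrees with the SAP's reduction of over 85%. The stated power of 80.7% reproduces with a one-sided, continuity-corrected normal approximation. With d = 0.043, the pooled-variance SE is √(2 × 0.0285 × 0.9715/232) = 0.01545 and the unpooled SE is √((0.05 × 0.95 + 0.007 × 0.993)/232) = 0.01532. Then Φ((0.043 − 1/232 − 1.645 × 0.01545)/0.01532) = 80.69%. That power is for an unadjusted test, so the choice of covariates does not alter it.

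**Primary endpoint.** The part of the risk ratio that runs through low birth weight is (1 + 0.10(k − 1))/(1 + 0.15(k − 1)). Dividing 0.14 by it gives the ratio after adjustment:

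| k | Part through low birth weight | Adjusted risk ratio |
|---|---|---|
| 1 | 1.000 | 0.140 |
| 2 | 1.10/1.15 = 0.957 | 0.146 |
| 5 | 1.40/1.60 = 0.875 | 0.160 |

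**Composite.** With low birth weight in a logistic model, low-birth-weight infants are predicted perfectly and contribute nothing to the group coefficient. The adjusted odds ratio is therefore the one among normal-weight infants.

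*Scenario A.*
- All infants: risks are 0.15 + 0.06 = 0.21 and 0.10 + 0.06 = 0.16. OR = (0.16/0.84)/(0.21/0.79) = 0.717.
- Normal-weight infants: risks are 0.06/0.85 = 0.0706 and 0.06/0.90 = 0.0667. OR = (0.06/0.84)/(0.06/0.79) = 0.940.
- Events: 232 × (0.21 + 0.16) = 85.8, against 232 × (0.06 + 0.06) = 27.8.
- SE of the log OR, all infants: √(1/48.72 + 1/183.28 + 1/37.12 + 1/194.88) = 0.241.
- SE of the log OR, normal-weight infants: √(1/13.92 + 1/183.28 + 1/13.92 + 1/194.88) = 0.393.

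*Scenario B.*
- All infants: risks are 0.21 and 0.10 + 0.04 = 0.14. OR = (0.14/0.86)/(0.21/0.79) = 0.612.
- Normal-weight infants: risks are 0.0706 and 0.04/0.90 = 0.0444. OR = (0.04/0.86)/(0.06/0.79) = 0.612.
- Events: 232 × (0.21 + 0.14) = 81.2, against 232 × (0.06 + 0.04) = 23.2.

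A second set of assumptions expresses preterm birth as a share of normal-weight infants. At 8% in both groups, low birth weight of 15% versus 10% gives an overall OR of 0.75, and 20% versus 12% gives 0.66. Both become 1.00 once low birth weight is held fixed. If the 8% also falls to 6% (low birth weight 15% versus 10%), 0.65 becomes 0.73.

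**Partner treatment.** The documents give no rate of partner treatment and no strength of association with transmission, so no size was computed.

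**Events available for the primary model.** 232 × 0.05 + 232 × 0.007 = 11.6 + 1.6, or about 13 transmissions in total.

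**The case against.** The SAP governs the adjusted comparison and names neither variable. Its rule covers risk factors for maternal STI and neonatal infection, which is narrower than Aim 2(b). The characteristics it monitors for balance (Methods for minimizing bias) are mostly baseline ones: sociodemographics, gestational age, HIV status, syphilis results and obstetric history. Aim 2(b) can be read as a separate predictor analysis, because section 3 sets it apart from 2(a), which carries the association with testing and treatment. The composite appears only in the SAP and low birth weight as a candidate covariate only in the protocol, so no single section plans to regress the composite on its own component. The sizes rest on assumed rates, and the primary power calculation uses a test without covariates.

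Much of this stands as a limit on the point. The plan does not commit to entering either variable, the benefit in section 11.d is worded as a possibility, and the unadjusted result is safe.

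It does not remove the point. Aim 2(b) sits inside the comparison aim and speaks of controlling for the factors it finds; nothing says that this happens in a separate model. The SAP's balance list is given as examples for monitoring, not as the adjustment set. Partner treatment is plausibly a risk factor for maternal STI, so it fits even the SAP's narrower wording.

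**Conclusion.** The concern holds. Neither document keeps low birth weight or partner treatment out of the adjusted group comparison, although both can follow from the intervention and low birth weight is itself an outcome. An analyst following the text could enter them.

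The risk is confined to the adjusted estimates. For the primary endpoint the bias through low birth weight is small over the assumed range. For the composite, the shift in the odds ratio runs from none to substantial, depending on whether preterm birth among normal-weight infants falls too. The loss of information appears in both scenarios, since roughly two thirds or more of the events drop out (86 to 28; 81 to 23). That the composite model would compare only normal-weight infants follows from the outcome definition and needs no assumed rate. The point should be fixed, but it does not undermine the planned unadjusted comparison.

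**What to change.** In Protocol section 2 (Aim 2(b)), Protocol section 3 (Specific Aim 2) and the SAP's statistical analysis section, state that adjusted analyses of testing versus standard care use only a short, named list of variables fixed before the enrolment test. Candidates already collected include age, HIV status, gestational age at enrolment, obstetric history, behavioural factors and partner characteristics at enrolment. The list must be short because only about 13 transmissions are expected.

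State also that low birth weight, other perinatal outcomes and partner treatment do not enter these models, and are examined only in a separate descriptive analysis of predictors of neonatal outcomes.

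The cost is wording in the two documents, with no new data. The one downside is that chance or clinic differences in low birth weight and partner treatment would no longer be adjusted for in the main adjusted model.
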